## 13.5 Safety Analyses

Safety and tolerability will be assessed by clinical review of all relevant parameters including adverse experiences (AEs), laboratory tests, and vital signs. Safety summaries will be reported for both cohorts. Death (other than death related to progressive disease) that occurs within 30 days of VB-111 administration will lead to pausing of the study and analysis of the toxicity data.

Adverse experiences (specific terms as well as system organ class terms) and predefined limits of change in laboratory, and vital sign parameters that are not pre-specified as events of interest will be summarized with descriptive statistics (counts, percentage, mean, standard deviation, etc.).

Continuous measures such as changes from baseline in laboratory, and vital signs parameters that

are not pre-specified as events of interest will be summarized using descriptive statistics (mean, standard deviation, etc.) for baseline, on-treatment, and change from baseline values.

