# **1.2** Primary Objectives & Hypotheses

**Primary Objective 1:** To evaluate the influence of VB-111 on tumor infiltrating T lymphocyte (TIL) density in recurrent/progressive GBM participants.

We hypothesize that neoadjuvant VB-111 will increase tumor infiltrating T lymphocytes within the tumor and enhance systemic tumor-specific T cell responses compared to adjuvant and control tumors.

**Primary Objective 2:** To evaluate the safety and tolerability of intravenous VB-111 in progressive/recurrent GBM participants undergoing surgery.

Safety analysis will be based on toxicities and grades as defined by CTCAE version 5.0 criteria, including serious adverse events (SAEs). The attribution to drug, time-of-onset, duration of the event, resolution, and any concomitant medications administered will be recorded. AEs analyzed include but are not limited to all AEs, SAEs, and fatal AEs.

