## 5.1 Treatment Regimen

Participants will be screened for eligibility up to 14 days prior to randomization. They will be sequentially randomized to one of three groups in a 1:1:1 ratio of the Neoadjuvant/Adjuvant arm (Group A), Adjuvant arm (Group B), and Control arm (Group C).

Group A (Neoadjuvant/adjuvant): Fifteen participants will receive VB-111 at 1x10^13 VPs intravenously 21±7 days prior to surgery. Tumor samples will be obtained at time of surgery, and tissue (fresh, frozen and FFPE) will be processed to achieve primary, secondary and exploratory objectives. Upon recovering from surgery (within 28-35 days after surgery), participants will resume single agent intravenous VB-111 every 6 weeks until tumor progression is supported by two consecutive time points of tumor growth (based on RANO criteria) or adverse event requiring discontinuation of study drug. Upon initial evidence of contrast-enhancing progression, and if clinically stable, participants may continue with VB-111 infusions. Bevacizumab or biosimilar may be used as supportive care if clinically indicated. Blood samples will be obtained as pharmacodynamics markers throughout the study. Dose holds and symptomatic management will occur based on preset adverse event determination. DLTs will not be determined. The toxicity evaluation period will begin with registration and extend to 30 days after the last treatment day. Participants will be followed for MRI changes, clinical exam and steroid doses from the registration period until the second progression. After tumor progression is confirmed on the second consecutive MRI, VB-111 will stop and participants will be followed every 3 months for vital status until death.

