### 5.3.2 Post-Surgery Dose Administration

For Group A and Group B, upon recovery from surgery (within 28-35 days after surgery), trial treatment should be administered after all procedures/assessments have been completed and reviewed as detailed on the Study Calendar (Section 10). Trial treatment may be administered up to 3 days before or after the scheduled infusion/injection day of each cycle due to administrative reasons.

All trial treatments should be administered on an outpatient basis. If the treating team would like to pursue treatment while inpatient, please contact the Overall Principal Investigator, [name], for prospective approval.

**Group A:** Participants will resume VB-111 every 6 weeks **Group B:** Participants will receive VB-111 every 6 weeks **Group C:** Participants will receive standard of care treatments

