## 13.1.2 Safety Endpoints

The primary safety endpoints are AEs graded using CTCAE version 5.0 criteria. Safety will be assessed by quantifying the toxicities and grades experienced by participants who have received VB-111, including serious adverse events (SAEs). Other safety endpoints include laboratory safety assessments, KPS status, vital signs and physical examinations.

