## **13.2** Definitions of Analysis Sets

- The Full Analysis Set (FAS) population will serve as the population for the analysis of primary efficacy endpoint TIL density in this study. The FAS population consists of all participants within each cohort who have received a preoperative dose of VB-111/placebo and had a surgery.
- The intention to treat (ITT) population is defined as all randomized participants. The ITT population will be used for secondary efficacy endpoints (PFS6, OS).
- The All Participants as Treated (APaT) population will be used for the analysis of safety data in this study. The APaT population consists of all allocated participants who received at least one dose of study treatment. At least one laboratory or vital sign measurement obtained subsequent to at least one dose of study treatment is required for inclusion in the analysis of each specific parameter. To assess change from baseline, a baseline measurement is also required.

A randomized, placebo controlled phase II, surgical trial to evaluate early immunologic pharmacodynamic parameters for the viral cancer therapy ofranergene obadenovec (VB-111) in patients with surgically accessible recurrent/progressive glioblastoma Version 3.0 February 18, 2021

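### Safety is to be summarised for two undefined cohorts in a three-group trial where Groups B and C switch agent after surgery, with no rule assigning events to agent or period

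*Combined protocol and SAP*

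**What the plan says.** Section 1.2 makes safety the second primary objective: "To evaluate the safety and tolerability of intravenous VB-111 in progressive/recurrent GBM participants undergoing surgery". Section 2.4.5.2 adds that both the pre- and the post-operative settings are of interest.

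The reporting unit is given in Section 13.5: "Safety summaries will be reported for both cohorts". The design in Section 5.1 is different: "They will be sequentially randomized to one of three groups in a 1:1:1 ratio".

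Two statements describe who is analysed. Section 13.1.2 has "Safety will be assessed by quantifying the toxicities and grades experienced by participants who have received VB-111". Section 13.2 has "The APaT population consists of all allocated participants who received at least one dose of study treatment", and Section 11.1.1 confirms that a placebo infusion is enough to be evaluable for toxicity.

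Before surgery, Section 5.3.1 gives VB-111 to Group A and placebo to Groups B and C. After surgery, Section 5.3.2 says for Group A "Participants will resume VB-111 every 6 weeks", for Group B "Participants will receive VB-111 every 6 weeks" and for Group C "Participants will receive standard of care treatments".

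**The concern.** Elsewhere in Section 13 (13.2 and 13.7) a cohort is simply a randomised group, and there are three of them. The sentence in Section 13.5 cannot be carried out as written, and whoever programs the tables must choose a reading.

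The choice matters because two of the three groups change agent part-way through, and the operation falls between the two phases. Adverse events are collected from the first infusion, placebo included (Section 7.5; Study Calendar note 19). The sponsor has singled out wound problems of grade 3 or higher for extra reporting (Section 7.3), and Section 7.1.1 lists wound dehiscence, cerebral hemorrhage and brain edema among events seen with VB-111. Brain surgery alone can produce the same events. A table that does not separate periods may charge surgical events on placebo to VB-111, or place VB-111 events in a control column.

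Randomisation also offers a placebo-controlled view of VB-111 around surgery, A against B+C. Section 13.6 lists between-group comparisons for survival, TIL density, gene signatures and IHC expression. Neither it nor Section 13.5 plans one for safety.

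**Working it through.** The plan gives no figure for the safety analysis, so there is none to reproduce. The check counts planned participants by agent and period, using 15 per group (Sections 5.1 and 13.3) and the sequences in Sections 5.3.1 and 5.3.2.

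| Group | n | Before surgery | After surgery |
|---|---|---|---|
| A | 15 | VB-111 | VB-111 |
| B | 15 | Placebo | VB-111 |
| C | 15 | Placebo | Standard of care |

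**Step 1: possible two-cohort splits.**
- A against B+C: the B+C column (30) holds 30 placebo courses, 15 VB-111 courses and 15 standard-of-care courses. B's post-operative VB-111 events sit with control.
- A+B against C: the A+B column (30) holds 15 pre-operative VB-111 courses, 15 pre-operative placebo courses and 30 post-operative VB-111 courses. B's placebo and surgical events sit with VB-111. C (15) mixes placebo with standard of care.
- Three columns with no period split: A is clean, but B and C each still mix two agents.

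No participant-level split separates the agents unless events are also divided by period.

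**Step 2: the two populations.** VB-111 recipients (13.1.2) number 15 + 15 = 30, and Group C drops out. APaT (13.2) numbers 15 + 15 + 15 = 45. The sections therefore imply different tables.

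**Step 3: length of the first period.** The infusion is 21±7 days before surgery, so 14 to 28 days. The first post-operative treatment comes 28 to 35 days after surgery. The total is 14 + 28 = 42 to 28 + 35 = 63 days. This leaves out the ±3-day administrative allowance in Section 5.3.2.

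**Step 4: how much of that period is blinded.** Section 5.4 blinds pre-operative treatment only. Appendix B, Section 3.7.4, sends the assignment to the site team once surgery is confirmed, a process that starts the day after the scheduled operation. The blinded part is thus about 14 to 28 days plus roughly a day. The post-surgical part is between 28/(28 + 28) = 50% and 35/(14 + 35) = 71% of the period.

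**Step 5: possible size of the distortion.** The documents give no event rates by period, so the rates here are assumed. Let a pre-operative event have rate p on VB-111 and q on placebo. Pooling A and B gives (15p + 15q)/30 = (p + q)/2. With p = 20% and q = 0 to 5%, the pooled rate is 10% to 12.5%. An event that surgery alone causes would shift in the other direction: B's cases would be added to the VB-111 count although B had received no VB-111.

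**The case against.** The strongest reply is that the wording is loose but nothing is lost. Section 1.2 has attribution and time of onset recorded, Section 7.2 sets a five-level attribution scale, and the coversheet in Appendix C asks separately about standard of care in Group C. Section 13.1.2 can also be read as counting only events after VB-111 was given. Section 13.5 plans clinical review and descriptive summaries with no test, so the layout is partly a matter of preference.

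Much of this stands, and it rules out several stronger readings that a reader might infer:
- That the events cannot be separated. The data allow it; the plan does not say that it will be done.
- That the plan states events will be pooled. It is silent, and mixing is a possible consequence of the missing rule.
- That all three groups change treatment. Group A resumes VB-111, and only B and C switch.
- That A against B+C is blinded up to the first post-operative dose. It is randomised throughout, but blinded only until surgery is confirmed.
- That 42 to 63 days means continuing placebo exposure. It is one saline infusion followed by observation. The figure measures a period, not a bias.

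The reply does not repair the reporting unit. Attribution is an investigator's judgment and does not replace a tabulation rule. The coversheet covers reportable events only.

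**Conclusion.** The point holds as a defect of specification on a primary objective, and the SAP should be amended. The reporting unit in Section 13.5 does not exist in this design, Sections 13.1.2 and 13.2 describe different populations (30 and 45 planned), and no rule assigns events to agent or period. Placebo-phase and surgical events may therefore be mixed with VB-111 events, and the randomised peri-operative contrast of 15 against 30 is unplanned.

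The counts are planned evaluable numbers. Actual safety denominators may be larger, because participants who are dosed but not operated on stay in APaT and are replaced for the primary analysis (Section 5.6). The dilution in Step 5 rests on assumed rates and only illustrates the direction and possible scale. No power or sample-size figure changes.

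**What to change.** In Section 13.5, replace the reference to cohorts with Groups A, B and C in the APaT set, and define two periods.

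- **Period 1:** from the first infusion to just before the first post-operative treatment. If none is given, the period ends when that participant's adverse-event collection ends. Show A, B and C, and A against B+C, including surgical and wound events. Report follow-up time, because routine collection stops 30 days (+7) after the last dose and is therefore shorter than 42 to 63 days in those with no post-operative dose. State that blinding covers only the part up to confirmation of surgery.
- **Period 2:** from the first post-operative treatment, by A, B and C. Flag events after supportive bevacizumab or biosimilar in A and B, and identify bevacizumab or biosimilar chosen as standard of care in C.
- **All-VB-111 summary:** Group A from its first infusion and Group B only from its first VB-111 dose.
- **Populations:** reconcile Section 13.1.2 with Sections 13.2 and 11.1.1.

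The cost is SAP wording and a few more descriptive tables with small denominators (about 15 against 30 in Period 1). No new data are needed and trial conduct does not change.

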# 2.3.2 Biodistribution

In preclinical evaluations, vector DNA was detected in all blood and tissue samples collected from mice in both non-tumor bearing and tumor bearing high dosed groups. The elimination rate was one magnitude of order in tissues and two magnitudes of order in blood between Day 5 and Day 91. Transgene expression was not found in non-tumor bearing mice. Expression was observed by RT-PCR only in lungs of tumor-bearing mice, demonstrating specificity of the treatment to the Lewis lung tumor mice [44].

In a completed phase 1 trial, mean levels of adenovirus vector DNA found in whole blood showed a dose-dependent effect. By 2 months after dosing, levels of Ad-5 decreased by at least 3-log or were undetectable. Detectable levels of Ad-5 in the urine were present only within the initial 6 hours after intravenous administration of VB-111. In a participant with esophageal cancer, transgene expression was found in subcutaneous metastasis aspirates up to Day 28 [45].

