# 5.4 Trial Blinding/Masking

Pre-operative treatment will be blinded; therefore, the treating investigator and subject will not know whether VB-111 or placebo is administered. An unblinded pharmacist or designee not involved in other study assessments will prepare the Pre-operative study drug of VB-111/Placebo. Post-operatively, treatment will be unblinded.

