# 8.1.9 Placebo

Normal Saline (NS) will be used as placebo in this study. NS will be provided by the study site.

A randomized, placebo controlled phase II, surgical trial to evaluate early immunologic pharmacodynamic parameters for the viral cancer therapy ofranergene obadenovec (VB-111) in patients with surgically accessible recurrent/progressive glioblastoma Version 3.0 February 18, 2021

Placebo should be kept at room temperature until administration. The following steps should be followed:

- Determine the volume to be applied according to the participant's weight (see Table 3).
- For patients who weigh >50kg: Place 50ml of saline (brought to room temperature) in a 60ml sterile syringe or select a 50ml saline bag.
- For patients who weigh <50kg: Place 35 ml of saline (brought to room temperature) in a 60ml sterile syringe
- After completing the preparation, record medication assigned to the participant in the participant dispensing log.

Placebo will be administered to participants assigned to Group B and Group C 21±7 days prior to surgery.

Both placebo and VB-111 infusion solutions are clear solutions that are visually indistinguishable. A dispensing log will be kept by the investigational pharmacist or designee, in which he/she will record the date(s) and details of the Placebo dispensed for each participant. The dispensing log will be made available to the study monitor who will verify accountability during the course of the study.

The preparation of the Neoadjuvant dose of VB-111/placebo will be performed by an unblinded site pharmacist or designee who is not involved in other study activities.

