Research blood 		X 	Х		Х		Х				Screening, Pre-surgery, Pre-Adjuvant Cycles, End of Tx
Archival Tissue and surgical tissue 			Х								Surgery
Post-EOT Therapies 								Х	Х	Х	30 day Post Drug, Active Follow-up, Long Term Follow-up
Survival 									Х	Х	Active Follow-up, Long Term Follow-up

A randomized, controlled, phase II surgical trial to evaluate early immunologic pharmacodynamic parameters for the viral cancer therapy ofranergene obadenovec (VB-111) in patients with surgically accessible recurrent/progressive glioblastoma Version 3.0 – February 18, 2021

- 1. All screening procedures to be performed within 14 days of randomization, except for informed consent, virology testing, and pregnancy test. Virology testing may occur up to 6 months prior to randomization (see footnote 24); Informed consent may occur up to 28 days prior to randomization (see footnote 11); and Pregnancy test for women of childbearing potential must be done within 72 hours prior to registration (see footnote 20).
- 2. Repeat laboratory testing if >3 days from screening laboratory evaluations.
- 3. Neo-adjuvant treatment with VB-111/Placebo must be initiated within 5 days of Randomization.
- 4. Screening assessments may serve as pre-surgery treatment assessment if < 14 days from the screening, except in the event that there are any indications that the participant's condition is deteriorating, for which laboratory evaluations should be repeated on the day of initiation of pre-surgery treatment. If > 14 days from screening assessment, laboratory evaluations should be repeated on the day of initiation of pre-surgery treatment.
- 5. For all post-surgery cycles, required assessments should be performed within 3 days of scheduled visit days.
- 6. Post-surgery window requirements: VB-111 must be administered 28-35 days from surgery. Assessments must be performed and reviewed prior to study agent administration.
- 7. End of treatment assessments to be performed within 7 days after last drug administration or within 7 days after decision to end treatment. Assessments may continue for ongoing reportable adverse events. Do not repeat the safety laboratory tests and physician exam if the previous assessments were completed within 14 days from the EOT visit.

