- 27. Pre-surgery VB-111/placebo administration is required for participants in all Groups 21±7 days prior to surgery. Group A and B will receive post-surgery VB-111 administration and it must start 28-35 days after surgery. Post-surgery VB-111 may be administered ±3 days from day 1 of each cycle. To avoid fever following study drug VB-111 administration, all patients will receive 1) 900-1000 mg of acetaminophen starting 1-2 hours prior to VB-111/Placebo dosing followed by 450-500 mg when necessary for up to 36 hours and 2) dexamethasone 4 mg 1-2 hours prior to VB-111/Placebo dosing followed by 4 mg for 3 days may be given if deemed necessary by the investigator.
- 28. Blood for biomarker evaluation: please see Table 4 Correlative Sample Summary for details on collection requirements.
- 29. Pre-study archival tumor tissue is to be submitted within 60 days of Randomization. Protocol surgery tissue is to be collected during the trial. Please see Table 4 Correlative Sample Summary for details on collection requirements.
- 30. Start/stop dates, names of treatment regimens and reason for stopping should be collected.
- 31. Date of death and reason should be collected for overall survival purposes, when applicable.
- 32. For all participants, if the post-surgery MRI is greater than 21 days from post-surgery VB-111 then MRI must be repeated on Cycle 1 Day 1. Starting from EOT visit, the participants will be followed up by radiologic imaging per standard of care.
- 33. The baseline research sample at the neoadjuvant time point must be drawn before treatment begins.
- 34. The Pre-Surgical Visit / Assessments will be done either on day of surgery or within 3 days prior to surgery.

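### The only automatic pause trigger counts 30 days from VB-111 dosing and has no anchor to surgery, which leaves about 12 to 33 post-operative days uncovered in Group A

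*Combined protocol and SAP*

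**What the plan says.** Section 13.5 (Safety Analyses) states: "Death (other than death related to progressive disease) that occurs within 30 days of VB-111 administration will lead to pausing of the study", to be followed by a review of the toxicity data. No other event in the plan pauses the study by itself; Section 5.1 says that dose-limiting toxicities will not be determined.

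The timing comes from the Study Calendar (Section 10). Footnote 27 says "Pre-surgery VB-111/placebo administration is required for participants in all Groups 21±7 days prior to surgery" and "Group A and B will receive post-surgery VB-111 administration and it must start 28-35 days after surgery". Footnote 6 gives the same post-operative interval: "VB-111 must be administered 28-35 days from surgery". Only Group A receives VB-111 before surgery. For the others, Section 8.1.9 says "Placebo will be administered to participants assigned to Group B and Group C 21±7 days prior to surgery".

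Primary Objective 2 (Section 1.2) is "To evaluate the safety and tolerability of intravenous VB-111 in progressive/recurrent GBM participants undergoing surgery". During the pre-operative phase, under Section 5.4, "the treating investigator and subject will not know whether VB-111 or placebo is administered". Appendix B, Section 3.7.4, releases the assignment to the site only after surgery has been confirmed.

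**The concern.** The pause rule takes its clock from dosing, while the safety question that is specific to this trial concerns dosing followed by surgery. The two clocks do not line up. The dose-based window is mostly used up before the operation, and no window is defined from the operation itself.

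Section 7.1.1 lists cerebral hemorrhage, brain edema, wound dehiscence and thrombosis among events seen with VB-111, all in its under-1% group. Nor do the documents show that exposure has ended by day 30. Section 2.3.2 describes the vector decline only at a later point: "By 2 months after dosing, levels of Ad-5 decreased by at least 3-log or were undetectable". It also reports transgene expression in one participant up to Day 28. None of this shows that deaths will occur after the window closes. It does show that the 30-day limit is not tied to the surgical risk period or to a documented end of exposure.

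The trigger also names VB-111 and not the blinded infusion. A death between the infusion and confirmation of surgery may or may not meet the rule, and Section 13.5 does not say who finds out. At stake is whether the sponsor's one automatic safeguard works during the period that a primary objective is about.

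**Working it through.** The plan states no operating characteristic for the pause rule, so there is no figure to reproduce. The check is date arithmetic.

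**Inputs**
- Pause window: 30 days from VB-111 (Section 13.5).
- Infusion to surgery: 21±7 days, so 14, 21 or 28 days (Section 5.3.1; Study Calendar footnote 27).
- Adjuvant VB-111 in Groups A and B: post-operative day 28 to 35 (footnotes 6 and 27).
- Planned evaluable participants: 15 per group, so 30 in Groups B and C (Sections 5.1 and 13.3).

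**Group A**

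Window closes on post-operative day = 30 − (infusion-to-surgery interval).
Gap = adjuvant dose day − closing day.

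| Infusion to surgery (days) | Window closes, post-op day | Gap if adjuvant dose on day 28 | Gap if adjuvant dose on day 35 |
|---|---|---|---|
| 14 | 30 − 14 = 16 | 28 − 16 = 12 | 35 − 16 = 19 |
| 21 | 30 − 21 = 9 | 28 − 9 = 19 | 35 − 9 = 26 |
| 28 | 30 − 28 = 2 | 28 − 2 = 26 | 35 − 2 = 33 |

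The range is 12 to 33 days, and 19 to 26 at the nominal interval. Counting only the full days strictly in between gives one day less in each cell.

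Example at the nominal interval: a death on post-operative day 5 is day 21 + 5 = 26 from the infusion and triggers the pause. A death on post-operative day 12 is day 21 + 12 = 33 and does not. At the 28-day interval, a death on post-operative day 5 is already day 28 + 5 = 33 and does not.

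**Groups B and C**

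Read literally, Group B has no VB-111 clock until post-operative day 28 to 35. Group C never receives VB-111, so its clock never starts.

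**Share of deaths outside the window (assumptions only)**

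The documents give neither a rate nor a timing for perioperative deaths. Two assumed timings over 30 post-operative days show how far the answer depends on them. With closing day c, the share missed by the pre-operative window is 1 − c/30 if deaths are uniform. It is 1 − (1 − e^(−c/m)) / (1 − e^(−30/m)) if deaths are exponential with mean m, truncated at 30 days.

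| Infusion to surgery (days) | c | Uniform | Exponential, m = 5 to 15 days |
|---|---|---|---|
| 14 | 16 | 47% | 4% to 24% |
| 21 | 9 | 70% | 16% to 48% |
| 28 | 2 | 93% | 67% to 86% |

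**The case against.** The strongest reply is that these deaths are neither unseen nor left waiting. Sections 7.5 and 7.6 collect deaths as serious adverse events until 90 days after the final study drug, with disease-progression events excepted. Table 2 sends them to the sponsor, the Coordinating Center and the manufacturer within 1 day of notification. Appendix B, Section 3.2, makes closures and temporary holds effective immediately, and Section 12.2 lets the DSMB recommend suspension. Wound events have their own safeguard. Those of grade 3 or higher are reported whatever their seriousness or expectedness (Section 7.3), within 2 business days if non-serious (Table 2), and the plan is to circulate them to investigators within 5 business days (Section 7.6). All of this stands. It confines the point to the automatic trigger, since the other routes depend on someone's judgement and have no stated threshold for a pause.

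The blinding objection also has force. The site pharmacist and the lead site's unblinded contact hold the assignment from randomization (Section 4.1; Appendix B, Sections 3.7 and 3.7.1), so the rule can be operated. What is missing is a sentence that sends the death to that person.

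A reader might go further and infer that the rule misses most perioperative deaths. The documents do not support this. Among the assumed timings above, most deaths are missed in every case only at the 28-day interval; at 21 days this holds only for uniform timing, and at 14 days for none. A reader might also infer that enrolment would run on until the next twice-yearly DSMB meeting. The 1-day reporting and the immediate-hold provision speak against that.

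**Conclusion.** The point holds as a gap in the automatic trigger. In Group A, 15 of the 45 planned evaluable participants, the trigger closes on post-operative day 2 to 16 and stays closed for about 12 to 33 days. This follows from the protocol's own dates and needs no outside assumption. The window then reopens at each adjuvant dose.

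For Groups B and C the conclusion rests on reading VB-111 in Section 13.5 literally, as excluding the placebo infusion. If the sponsor meant the rule to cover every blinded infusion, the text should say so, and the Group A arithmetic would then apply to all three groups.

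The size is a number of uncovered days, not a number or share of missed deaths. Given the other reporting routes, this is an inexpensive improvement to a safeguard that the sponsor already chose to have. It is not evidence that participants would go unmonitored.

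**What to change.** Amend Section 13.5 and reconcile it with Sections 5.3.1 and 5.4 and with Appendix B, Section 3.7.4:

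- Anchor the pause trigger to the protocol surgery as well as to VB-111 dosing, so that it covers the interval up to the first adjuvant dose. The sponsor should set the exact window.
- Keep the consequence as a pause of the whole study. A pause of enrolment alone would be weaker than the present text.
- State whether the rule applies to participants whose pre-operative infusion was placebo.
- State that a death after a blinded infusion goes to the existing unblinded contact, who determines whether the rule applies and informs the DSMB.

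The cost is a short amendment and possibly an extra brief pause. If placebo recipients are included, an assumed mortality of 1% to 3% gives 30 × 0.01 = 0.3 to 30 × 0.03 = 0.9 pauses over the trial. The mortality is an assumption, because the documents give none. The count would rise slightly if unevaluable participants are replaced, as Section 5.6 allows.
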